9.2.2 Primary endpoint(s) analyses

The number and proportion of participants who achieve ORR per IRC assessment will be calculated for each group. The relative risk of Isa-SC + Pd relative to Isa-IV + Pd and its two-sided 95% CI using Farrington and Manning method will be provided. If the lower bound of the 95% CI is not less than a non-inferiority margin of 0.839, the non-inferiority of efficacy Isa- SC + Pd relative to Isa- IV + Pd will be concluded. The odds ratio of ISA- SC+ Pd relative to Isa- IV + Pd with their 95% CI will also be provided.

For the co-primary PK endpoint of C_{trough} at steady state (corresponding to predose at C6D1), summary statistics such as geometric means, coefficient of variation, median and range will be provided for treatment group. The ratio of the geometric means of Isa-SC+ Pd relative to Isa- IV + Pd and corresponding two-sided 90% CI will be provided by calculating the 90% CI under the logarithm scale then converting back to its original scale. The non-inferiority of PK Isa- SC + Pd relative to Isa- IV + Pd will be concluded if the lower bound of the 90% CI for the geometric mean ratio of C_{trough} at steady state is at least 80% (a non-inferiority margin of 80%).

The non-inferiority of ISA- SC+ Pd relative to Isa- IV + Pd will be concluded if both the efficacy and PK endpoints achieve non-inferiority.

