9.2.1 General considerations

Myeloma response and progression will be determined by Independent Review Committee based on central laboratory M-protein analysis and central radiology review using IMWG 2016 criteria.

The following stratification factors will be used:

- MM isotype (IgG versus non-IgG).
- Body weight (≤ 65 kg, > 65 to ≤ 85 kg, and > 85 kg).
- Number of prior lines (1-2 versus ≥ 3).

Primary and secondary endpoints will be analyzed by treatment arm.

Study treatment is defined as isatuximab (SC/IV) in combination with pomalidomide and dexamethasone. First dose of study treatment is defined as the first starting dose of any study intervention of isatuximab, pomalidomide or dexamethasone. Last dose of study treatment is defined as the last dose of any study intervention of isatuximab, pomalidomide, or dexamethasone.

For each of the safety parameters, the baseline will be defined as the last value or measurement taken up to the first dose of study treatment.

The observation period will be divided into 3 segments:

- The **pre-treatment** period is defined as the time the ICF is signed until the first dose of the study treatment administration.
- The **treatment-emergent (TE) period** is defined as the period from the first study treatment administration to the last study treatment administration +30 days.
- The **post-treatment period** is defined as the time starting 31 days after the last study treatment is administered to study closure or death, whichever comes first.

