9.2.3 Secondary endpoint(s) analyses

9.2.3.1 Key Secondary Endpoints

VGPR or better rate per IRC assessment will be summarized for the ITT population in the same way as for ORR endpoint. The non-inferiority test for non-unity null according to Farrington and Manning (1990) will be performed for VGPR or better rate. The non-inferiority margin is 0.6312 which was calculated as 40% retention of the observed historical clinical benefit of VGPR or better ratio 0.478 (upper bound of the 95% CI of rate ratio for Pd over CD38+ Pd as demonstrated in ICARIA-MM trial) under the logarithm scale then converting back to its original scale. If the lower bound of the 95% CI is not less than a non-inferiority margin of 0.6312, the non-inferiority of Isa-SC + Pd relative to Isa- IV + Pd on the VGPR or better rate will be concluded.

The PK endpoint of CT4W will be summarized for the CT4W-PK population in the same way as for the C_{trough} at steady state endpoint. The non-inferiority of Isa- SC + Pd relative to Isa-IV + Pd on CT4W corresponding to predose at C2D1 will be concluded if the lower bound of the 90% CI for the geometric mean ratio of CT4W is at least 80% (a non-inferiority margin of 80%).

Incidence rate of IRs will be compared between treatment arms on the safety population using the Fisher's exact test. The relative risk, odds ratio of ISA- SC+ Pd relative to Isa- IV + Pd with their 95% CI will be provided.

Percentage of participants who reported satisfied or very satisfied with the injection method used to administer the study medication based on the PESQ questionnaire at C5D15 visit will be compared between treatment arms on the ITT population using the stratified CMH method.

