9.5 SAMPLE SIZE DETERMINATION

A total sample size of 534 participants (randomization ratio 1:1, ie, 267 randomized participants in the SC arm, and 267 randomized participants in the IV arm) was determined to demonstrate non-inferiority of SC arm versus IV arm on the proportion ratio of participants who achieved ORR, and the geometric mean ratio of C_{trough} at steady state (corresponding to predose at C6D1). For the co-primary efficacy endpoint of ORR, the non-inferiority test for non-unity null according to Farrington and Manning (1990) was implemented. With 2.5% one sided Type I error rate, and a non-inferiority margin of 0.839 which was calculated as 40% retention of the observed historical clinical benefit of ORR ratio 0.7463 (upper bound of the 95% CI of rate ratio for Pd over CD38+Pd as demonstrated in ICARIA-MM trial) under the logarithm scale then converting back to its original scale, 534 randomized participants provide approximately 80% power for this

efficacy co-primary endpoint assuming that ORR for IV arm is 60.4% and the true response rate ratio is 1.02 for SC arm over IV arm. For the PK co-primary endpoint of C_{trough} at steady state, assuming C_{trough} at steady state follows log normal distribution with a true geometric mean ratio of 1 and a CV of 75%, and an assumed drop-out rate of no more than 50% to the PK per-protocol population, 534 randomized participants will provide at least an 86% power to show the lower bound of the 90% CI of the geometric mean ratio of C_{trough} at steady state is at least 80% (a non-inferiority margin of 80%).

Calculations were made based on SAS 9.4 ([1](#)).

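### ORR and VGPR are tested by a relative-risk method written without strata although randomisation is stratified; the test is valid, but a stratified score interval would recover a little precision

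*Protocol*

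**What the plan says.** Protocol Section 6.3.2 stratifies randomisation by MM isotype (2 levels), body weight (3 levels) and number of prior lines (2 levels), which makes 12 cells. Section 9.2.1 lists the same three factors under the words "The following stratification factors will be used", without naming an analysis.

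For the ORR co-primary, Section 9.2.2 specifies the relative risk of SC to IV, and its "two-sided 95% CI using Farrington and Manning method will be provided". Non-inferiority is decided by comparing the lower bound with 0.839. The synopsis and the estimand table (Table 7) name the same method. For the first key secondary endpoint, Section 9.2.3.1 says "VGPR or better rate per IRC assessment will be summarized for the ITT population in the same way as for ORR endpoint", again by Farrington-Manning, with a margin of 0.6312. None of these places mentions strata.

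The last key secondary endpoint, satisfaction on the PESQ, is "compared between treatment arms on the ITT population using the stratified CMH method". It is the only comparison in Section 9.2 that is called stratified.

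The power statement in Section 9.5 reads "With 2.5% one sided Type I error rate, and a non-inferiority margin of 0.839", and then "534 randomized participants provide approximately 80% power for this" endpoint, "assuming that ORR for IV arm is 60.4" per cent and "the true response rate ratio is 1.02 for SC arm over IV arm".

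**The concern.** Stratified randomisation balances the arms on the three factors, so differences in response between strata contribute little to the true sampling error of the arm comparison. A crude two-sample standard error still counts that between-stratum variation. If the factors predict response, the crude interval is somewhat too wide and the test runs below its nominal level.

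This matters most for ORR. Both co-primaries must succeed, and ORR has the lower planned power (about 80%, against at least 86% for the PK endpoint). The gap between Section 9.2.1 and Sections 9.2.2 and 9.2.3.1 also leaves it unclear what the factors are for.

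**Working it through.** **Inputs.** From Section 9.5: 267 per arm, IV response p2 = 0.604, true ratio 1.02 (so p1 = 0.604 × 1.02 = 0.61608), margin R = 0.839, one-sided 2.5%. From Section 6.3.2: 12 strata. Stratum shares and stratum response rates are not in the protocol and are assumed below.

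**Step 1: reproduce the stated power with the crude test.** The Farrington-Manning statistic is

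z = (p1 − R·p2) / √[ t1(1−t1)/n + R²·t2(1−t2)/n ],

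where t1 and t2 are the response rates estimated under t1 = R·t2.

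- Restricted rates: t1 = 0.5495, t2 = 0.6550.
- Null SE: √[(0.5495×0.4505 + 0.839²×0.6550×0.3450)/267] = 0.03902.
- SE under the alternative: √[(0.6161×0.3839 + 0.839²×0.604×0.396)/267] = 0.03894.
- Distance from the null: 0.61608 − 0.839×0.604 = 0.10932.
- Power: Φ[(0.10932 − 1.96×0.03902)/0.03894] = Φ(0.843) = 80.05%.

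267 per arm is the smallest size that reaches 80%. The planned power is therefore that of a plain two-sample test, which supports reading Section 9.2.2 as unstratified.

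**Step 2: what stratification removes.** If the true response rate has standard deviation s between strata, stratifying removes a fraction of about s²/[p(1−p)] of the variance, with p(1−p) = 0.604×0.396 = 0.2392.

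| Assumed s | Variance removed | Equivalent n per arm | Power of a stratified test |
|---|---|---|---|
| 0 | 0% | 267 | 80.0% |
| 0.05 | 1.0% | 270 | 80.5% |
| 0.10 | 4.2% | 279 | 81.7% |
| 0.15 | 9.4% | 295 | 83.8% |

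These are not net gains. Under stratified randomisation the crude test's power also rises a little as s grows, so the two tests must be compared on the same simulated trials.

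**Step 3: crude against stratified score test for ORR.** The stratified statistic sums w(p1 − R·p2) over strata, with weights based on stratum size, restricted-estimate variances and an N/(N−1) correction. Assumed shares are isotype 60/40, weight 30/40/30 and prior lines 65/35, with 200,000 trials per row.

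| Assumed range of ORR over strata | Crude power | Stratified power | Gain (points) | Crude type I error |
|---|---|---|---|---|
| no difference | 80.2% | 80.1% | −0.1 | – |
| 47–71% | 80.4% | 80.8% | 0.4 | 2.4% |
| 38–77% | 80.8% | 82.0% | 1.2 | 2.3% |
| 31–82% | 81.3% | 83.4% | 2.1 | 2.1% |

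The stratified test stays at about 2.5% throughout. A second simulation of 100,000 trials per scenario gave crude against stratified power of 80.0 vs 79.9% with no stratum effect, then 80.4 vs 80.7%, 80.6 vs 81.7% and 81.2 vs 83.6% as effects grew. The largest gain is 83.6 − 81.2 = 2.4 points.

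**Step 4: VGPR or better.** With 31.8% in the IV arm (the ICARIA-MM figure in Section 2.2.3.1), an assumed true ratio of 1.0 and the stated margin of 0.6312, the crude test already has 94.6% power. Little is left to gain, and the simulated gain is under 1 point. The type I error of the stratified score test is 2.4–2.6% for ORR and VGPR alike.

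**The case against.** **Unstratified is inferred.** The protocol never uses the word for ORR, Section 9.2 calls itself a summary, and the SAP, which was not available here, may settle the matter. That is fair as far as it goes. But the protocol itself fixes the interval method and the decision rule for a co-primary endpoint, says stratified where it means it (PESQ), and bases its power on the two-sample test. Plain Farrington-Manning is the natural reading of a stated method, so this is not a missing detail.

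**A flat contradiction.** A reader might infer that Sections 9.2.1 and 9.2.2 contradict each other. They do not, because Section 9.2.1 ties the factors to no particular analysis. It is unclear, not inconsistent.

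**Invalid or underpowered.** A reader might also infer that the crude test inflates error or leaves the trial short of power. Neither is supported. Its error is at or slightly below nominal, which in a non-inferiority trial errs on the cautious side, and the stated 80% reproduces without stratification.

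**The gain is assumed.** This stands. The protocol gives no response by isotype, weight or prior lines. It has pointers: higher exposure in non-IgG participants (Section 2.2.3.2), and exposure varying with weight together with a strong link between CT4W and efficacy (Section 4.4.2). Section 2.1 cites ORRs of 60% and 69% for daratumumab with Pd after at least two and at least one prior lines, but these come from different trials, and the same section expects similar isatuximab efficacy at first relapse. None of this fixes a size.

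**Stratifying has its own costs.** Twelve cells average 267/12 ≈ 22 per arm. On the assumed shares the smallest cell is 0.40×0.30×0.35 = 0.042 of the sample, about 11 per arm, with 3 to 4 VGPR responders at 31.8%. The method also matters: a Mantel-Haenszel ratio with a Wald interval ran at 2.77% in its strongest scenario. The score version held its level, so this argues for naming the score method and its weights, not against stratifying.

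**Conclusion.** The point holds as a minor improvement in efficiency and clarity. The crude Farrington-Manning comparison is valid and agrees with the sample-size basis. It becomes slightly conservative if the randomisation factors predict response. Against a stratified score test it then gives up about 0 to 2.5 power points for ORR and under 1 point for VGPR.

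These sizes rest on assumed stratum shares and stratum effects; with no stratum effects the two tests perform alike. The documents do not support any claim that the trial's conclusion is at risk or that a worthwhile gain is certain.

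**What to change.** 1. In Sections 9.2.2 and 9.2.3.1 and the synopsis, with Table 7 aligned, make a stratified score interval for the relative risk (Farrington-Manning/Miettinen-Nurminen type) the deciding analysis for ORR and VGPR or better.
2. Use the strata recorded in the IRT and weights n1·n0/N per stratum. With near-equal allocation within strata these weights follow stratum size, so the overall contrast stays close to the marginal one to which the margin refers.
3. Pre-state a pooling rule for sparse cells: a minimum cell size and an order of collapsing, set without reference to response by arm.
4. Keep the crude Farrington-Manning interval as a sensitivity analysis.
5. In Section 9.2.1, name the analyses that use the three factors.

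Margins and sample size stay as they are. The cost is a few sentences, one pooling rule and slightly more analysis work, with no new data. It should be settled before anyone compares response between arms.

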The safety population will include ITT participants who have received at least 1 dose or a part of a dose of the study intervention. All analyses using this population will be based on the treatment actually received.

All safety analysis will be performed on this population.

PP-PK population

The PP-PK population will include all randomized participants which have received at least eleven Isatuximab doses out of twelve up to C5D15 (one dose omission permitted during Cycle 1), with isatuximab C6D1 (predose) concentration results from PK sample collected within the defined per protocol time window and adequate documentation of dosing and sampling dates and times.

This population will be used for the analysis of the co-primary PK endpoint.

CT4W-PK population

The CT4W - PK population for CT4W endpoint will include all randomized participants having completed administration of all the first 4 weekly isatuximab doses at Cycle 1, with isatuximab C2D1 (predose) concentration results from PK sample collected within the defined per protocol time window and adequate documentation of dosing and sampling dates and times.

This population will be used for the analysis of the CT4W PK endpoint.

Primary analysis

The number and proportion of participants who achieve ORR per IRC assessment will be calculated for each group. The relative risk of Isa-SC + Pd relative to Isa-IV + Pd and its two-sided 95% CI using Farrington and Manning method will be provided. If the lower bound of the 95% CI is not less than a non-inferiority margin of 0.839, the non-inferiority of efficacy Isa-SC + Pd relative to Isa-IV + Pd will be concluded.

For the co-primary PK endpoint of C_{trough} at steady state (ie, C6D1 predose), summary statistics such as geometric means, coefficient of variation, median and range will be provided for treatment group. The ratio of the geometric means of Isa -SC + Pd relative to Isa-IV + Pd and corresponding two-sided 90% CI will be provided by calculating the 90% CI under the logarithm scale then converting back to its original scale. The non-inferiority of PK Isa-SC + Pd relative to Isa-IV + Pd will be concluded if the lower bound of the 90% CI for the geometric mean ratio of C_{trough} at steady state is at least 80% (a non-inferiority margin of 80%).

The non-inferiority of Isa-SC+ Pd relative to Isa-IV + Pd will be concluded if both the efficacy and PK endpoints achieve non-inferiority.

Analysis of key secondary endpoints

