After the first Isa-SC administration, the median time to reach maximum concentration (C_{max}) was approximately 95 hours. The C_{max} and area under the plasma concentration time curve over the first week (AUC_{1week}) were comparable after the first 1000 mg and 1400 mg Isa-SC dose whichever the Isa-SC delivery method used (IP or OBDS) and were lower than those observed after 10 mg/kg IV administration (Table 4) which is in agreement with the slow absorption observed for the SC administration route. Similar results were observed after the seventh Isa-SC administration in the QW/Q2W regimen, with comparable area under the plasma concentration time curve over two weeks of dosing (AUC_{2weeks}) after 1000 mg and 1400 mg SC doses.

A moderate interpatient variability was observed for exposure after the first Isa-SC administration (total coefficient of variation [CV] for C_{max} , AUC_{1week} or C_{trough} of 33% to 52%) or after the seventh Isa-SC administration (total CV for C_{max} , AUC_{2weeks} or C_{trough} of 38% to 65%) with the IP and remained of the same extent when using the OBDS (total CV for C_{max} , AUC_{2weeks} or C_{trough} of 33% to 52%). The total variability appeared to be slightly higher for the 1400 mg SC-OBDS cohort versus 1400 mg SC-IP cohort but it remained comparable to the one observed for 1000 mg SC-IP cohort.

Previous population PK analysis (POH0503) with IV data has shown that participants with less aggressive disease at baseline are expected to have lower linear clearance (CL) and therefore higher exposure; similarly, non-IgG participants have higher exposure than the IgG participants. The unbalanced covariates distribution between the SC cohorts explains the comparable exposure between these cohorts with participants from the 1000 mg SC-IP cohort having less

advanced disease, lower tumor burden (higher albumin, lower β 2 microglobulin level, International Staging System [ISS] stage, M-protein level and bone marrow plasma cell [BMPC]) than the 1400 mg SC cohorts. The covariates distribution between 1400 mg cohorts (IP and OBDS) was similar with the exception of body weight. For the weight, the distribution was similar between participants of 1000 mg SC-IP and 1400 mg SC-OBDS cohorts, but patients in the 1400 mg SC-IP cohort were heavier.

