The mean (\pm standard error [SE]) C_{trough} over time after IV and SC isatuximab QW/Q2W show comparable C_{trough} profiles after 1000 mg and 1400 mg SC which were higher than those observed after 10 mg/kg IV. Relative to first administration, the accumulation ratio based on C_{trough} ranged from 2.65 (1400 mg SC-OBDS) to 3.64 (1000 mg SC-IP) for Cycle 2 Day 1 (fifth administration) and from 2.83 (1400 mg SC-OBDS) to 4.04-fold (1000 mg SC-IP) for Cycle 4 Day 1 (ninth administration) after the SC administration (1000/1400 mg with IP or OBDS). Accumulation was comparable to that observed after IV administration, with accumulation ratio of 3.96 for Cycle 2 Day 1 and of 3.60 for Cycle 4 Day 1.

It is important to note that individual CT4W values (best PK predictor of efficacy) after 1000 mg SC-IP and 1400 mg SC-IP or OBDS QW/Q2W regimens were similar or higher than those observed in patients treated by IV route at 10 mg/kg QW/Q2W, with comparable inter-patient variability (Table 4).

Table 4 - Mean (CV%) isatuximab PK parameters after the 1st and 4th SC administration at 1000 mg or 1400 mg QW/Q2W and after the IV administration at 10 mg/kg in TCD15484 – non compartmental analysis

Study	Dose/Route	Number of patients	C_{max} (µg/mL)	t_{max}^a (h)	CT1W (µg/mL)	AUC_{1week} (µg.h/mL)	CT4W (µg/mL)
TCD15484*	1000 mg SC-IP	12	119 (48)	91.90 (46.20-168.00)	101 (44) ^b	15200 (52) ^b	339 (26) ^c
	1400 mg SC-IP	10	104 (33)	92.60 (68.40-168.00)	92.3 (31) ^d	12900 (36)	338 (36) ^e
	1400 mg SC-OBDS	22	145 (49)	95.10 (46.90-192.00)	128 (46)	17400 (49)	326 (46) ^f
	1400 mg SC (OBDS+IP)	32	132 (49)	94.70 (46.90-192.00)	118 (46) ^g	16000 (48)	330 (42) ^h
TCD15484*	10 mg/kg IV	12	234 (29)	3.63 (3.33-11.30)	56.8 (48) ^b	19300 (28)	235 (40) ^d

CT4W were used in descriptive statistics calculation even if patients did not receive the 4 doses at Cycle 1.

Abbreviations: AUC_{1week} = area under the plasma concentration time curve over the first week; C_{max} = maximum concentration; C_{trough} = predose concentration during repeated dosing; CT1W = C_{trough} at 1 week; CT4W = C_{trough} at 4 weeks; t_{max} = time to reach C_{max} ; NR = No Result.

a Median(min-max),

b N = 11,

c N = 8,

d N = 9,

e N = 6,

f N = 13,

g N = 31,

h N = 19,

*based on NCA analysis.

2.2.3.3 *Pomalidomide*

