6.3.2 Randomization

All eligible participants will be randomly assigned to a treatment group (either SC or IV arm) in a 1:1 ratio using an IRT. Participant assignment to a treatment group will be performed according to a stratified randomization list as follows:

- MM isotype (IgG versus non-IgG).
- Body weight (≤ 65 kg, >65 - ≤ 85 kg, and >85 kg).
- Number of prior lines (1-2 versus ≥ 3).

After each participant has completed the necessary screening visit procedures, the corresponding baseline eCRFs have been completed and the participant is deemed eligible for randomization by the Investigator or designee based on the laboratory evaluations as defined in the study flow chart ([Section 1.3](#)), the study site will contact the IRT.

Study intervention will be dispensed at the study visits summarized in the schedule of activities (SoA).

WARNING: Randomization will be blocked if study treatment is not available at site level. A minimum of time will be required between screening registration call and study treatment delivery at site level. Please consider this time between screening call and randomization call, which is indicated in the IRT manual.

Study treatment should be initiated within 3 working days after randomization.

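### Optional gain, low severity: the C6D1 trough ratio is described without covariates, and adjusting for the randomisation factors would tighten it at almost no cost

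*Protocol*

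**What the plan says.** Protocol Section 9.2.2 gives the PK co-primary rule: take the ratio of geometric means SC/IV at C6D1 predose, with the "corresponding two-sided 90% CI will be provided by calculating the 90% CI under the logarithm scale then converting back to its original scale", and conclude non-inferiority if the lower bound is at least 80%. The synopsis repeats the method: the interval "will be provided by calculating the 90% CI under the logarithm scale then converting back to its original scale". Neither place names a covariate or a stratified analysis. Section 9.2.3.1 carries the method over to the four-week trough: "The PK endpoint of CT4W will be summarized for the CT4W-PK population in the same way" as the steady-state trough.

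The randomisation is stratified. Section 6.3.2 states: "Participant assignment to a treatment group will be performed according to a stratified randomization list as follows", and then lists isotype (IgG or non-IgG), body weight in three bands and prior lines in two groups. Section 9.2.1 introduces the same three factors with "The following stratification factors will be used" but does not tie them to any analysis. Within Section 9.2 only the satisfaction comparison is expressly stratified, by a CMH method.

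On whether the factors matter for exposure, Section 2.2.3.2 reports from population PK work that "non-IgG participants have higher exposure than the IgG participants". It gives the direction and no size.

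Section 9.5 powers the endpoint "with a true geometric mean ratio of 1 and a CV of 75"%, allows up to 50% loss to the PP-PK population, and states at least 86% power.

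**The concern.** When arms are balanced by design on a factor that predicts the outcome, that factor contributes little to the chance difference between arms. An unadjusted standard error still counts its variance as noise, so the interval comes out a little wider than it need be. Isotype is such a factor here: it is randomised on, and the protocol says it shifts exposure.

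Both co-primary endpoints must succeed for the trial to claim non-inferiority, so precision on the PK endpoint bears directly on the result. The factors are already collected for the randomisation, and on the log scale a linear model with these terms targets the same geometric mean ratio. What is at stake is some unused precision, not the validity of the test.

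**Working it through.** **Inputs.** From Sections 9.2.2 and 9.5: margin 0.80, so log margin = ln(1/0.80) = 0.2231; lower bound of a two-sided 90% CI, so one-sided 5%; true ratio 1; CV 75%; 267 per arm with up to 50% loss, so about 133 per arm analysed. From Section 2.2.3.2: CV 33% to 52% with the on-body device. That section's 38% to 65% range belongs to the infusion pump, which this trial does not use, so it is left out.

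**Reproducing the plan's figure (no covariate).**
- SD(log) = sqrt(ln(1 + 0.75²)) = 0.668.
- SE = 0.668 × sqrt(2/133) = 0.0819.
- Noncentral t with 264 df and noncentrality 0.2231/0.0819 = 2.72 gives power 85.8%. The normal approximation gives 86.0%.
- The stated 86% is therefore reproduced by an unadjusted calculation at one-sided 5%.

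**With adjustment.** Multiply SD(log) by sqrt(1 − R²) and use 260 df: isotype takes 1, weight 2 and prior lines 1, so 4 fewer. R² is the share of log-scale variance the factors explain. The protocol gives no value, so 5%, 10% and 20% are assumed.

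| 133 per arm | Unadjusted | R² 5% | R² 10% | R² 20% |
|---|---|---|---|---|
| CV 75%, true ratio 0.95 | 67.3% | 69.2% | 71.2% | 75.6% |
| CV 75%, true ratio 1 (plan) | 85.8% | 87.3% | 88.9% | 91.8% |
| CV 75%, true ratio 1.1 | 98.7% | 99.0% | 99.3% | 99.6% |
| CV 75%, true ratio 1.2 | >99.9% | >99.9% | >99.9% | >99.9% |
| CV 52%, true ratio 1 | 98.1% | 98.5% | 98.8% | 99.4% |
| Smallest observed ratio that passes, CV 75% | 0.916 | 0.913 | 0.910 | 0.903 |

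The last row is 0.80 × exp(t × SE).

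**Is that R² range plausible from isotype alone?** For a two-level factor, R² = p(1 − p)(ln r)²/0.446, where p is the non-IgG share, r is the non-IgG to IgG exposure ratio and 0.446 = 0.668². Both p and r are assumptions. With p from 20% to 40%, r = 1.25 gives about 2% to 3%, r = 1.5 gives 6% to 9%, and r = 2.0 gives 17% to 26%.

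**Error rate.** In simulated stratified trials with the whole effect placed on isotype and 50% lost at random, the one-sided error at a true ratio of 0.80 was 5.0%, 4.6% and 4.0% unadjusted, and 5.1%, 4.9% and 5.0% adjusted, for R² of 5%, 10% and 20%. The unadjusted test never exceeded its level. With R² = 0, simulated power went from 85.3% to 85.0%, so the cost of useless covariates is about 0.3 points.

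**Body weight.** Section 4.4.2 reports simulations in which exposure falls with weight under flat SC dosing and rises with weight under weight-based IV dosing. A common weight term cannot describe opposite slopes. A simulation with that reversal built in still kept the adjusted error near 5% (5.2%, against 4.5% unadjusted), and power rose from 89% to 91%. The weight term is harmless here but may add little.

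**The case against.** The strongest reply is that the protocol contains nothing to correct. Section 9.2 calls itself a summary and leaves technical detail to the SAP. The wording in Section 9.2.2 does not exclude a model with covariates, and Section 9.2.1 leaves room for one. Sizing a trial without counting on covariate gain is ordinary cautious practice and does not fix the analysis model. This stands: the point is a suggestion to specify the model, and it falls away if the SAP already adjusts.

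The reply also says the gain is small or absent on the protocol's own data, and that stands too. R² is assumed throughout. At the on-body device's CV the test is already near 98% power. Section 2.2.3.2 reports SC troughs "which were higher than those observed after 10 mg/kg IV", with mean four-week troughs in Table 4 of 330 and 235 µg/mL (330/235 = 1.40). Those are small cohorts at a different time point, but if a similar excess holds at C6D1, adjustment changes nothing of consequence.

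The objection that the reversed weight trend makes the adjusted model unsafe does not stand, given the simulated error rate. It does limit the expected gain mainly to isotype. Section 8.3 already plans population PK work on weight and exposure, so no further weight analysis is asked for here.

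A reader might infer from the list in Section 9.2.1 that the protocol contradicts itself by omitting the factors in Section 9.2.2, or that the unadjusted interval misstates the error rate. Neither is supported. Section 9.2.1 assigns the factors to no particular analysis, and the unadjusted error stays at or below its nominal level.

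**Conclusion.** The point holds as an optional gain in precision, of low severity. As written, the PK co-primary analysis is valid, reproduces its stated power and is at most slightly conservative. At the planning values, adjustment would add about 1.5, 3 or 6 percentage points of power (R² 5%, 10% or 20%). At CV 52% it would add 0.4, 0.7 or 1.3 points, and at a true ratio well above 1 almost nothing. It is worth having mainly if the true ratio is near or below 1 and variability is close to the planned 75%.

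These sizes rest on the assumed R², on 133 per arm analysed and on log-normal troughs. Isotype is the only randomisation factor for which the documents clearly support a gain. Nor does adjustment deal with selection into the PP-PK population, from which up to half of participants may be missing: it can reduce the effect of chance imbalance on the factors among those analysed, but not bias from who remains.

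**What to change.** In Section 9.2.2, in Section 9.2.3.1 for the four-week trough, and in the synopsis, state that the geometric mean ratio and its 90% CI come from a linear model on log concentration with treatment and the three randomisation factors, back-transformed. Keep the unadjusted ratio as a sensitivity analysis. The margin, decision rule and sample size stay as they are. If the SAP already specifies such a model, it is enough to align the protocol wording with it.

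The cost is wording in three places and four degrees of freedom, with no new data. If the factors explain nothing, about 0.3 points of power are lost. The choice should be fixed before the primary analysis.
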